### 16.3 Analysis Plan

The analysis for this trial will commence at planned time points (see 16.2) and at the time the patients have become evaluable for the primary endpoint. The Statistician and Study Chair will make the decision, in accord with CCS Standard Operating Procedures, availability of data for secondary endpoints (e.g., laboratory correlates), and the level of data maturity. In each arm, it is anticipated that the earliest date in which the results will be made available via manuscript, abstract, or presentation format is when last patient in that arm has been followed for at least 6 months.

16.31 Primary Outcome Analyses (to be evaluated in each arm independently): :

16.311 Definition: The primary endpoint in each arm of this trial is the proportion of patients who achieve a confirmed complete response. A confirmed complete response is defined as an sCR or CR noted as the objective status on two consecutive evaluations at least two weeks apart. All patients meeting the eligibility criteria who have signed a consent form and have begun treatment will be evaluable for response, unless they are determined to be a major violation.

16.312 Estimation: The proportion of successes in each arm will be estimated by the number of successes divided by the total number of evaluable patients. An exact binomial 95% confidence interval for the true success proportion will be calculated.

16.313 Over Accrual: If more than the target number of patients are accrued, the additional patients will not be used to evaluate the stopping rule or used in any decision making processes; however, they will be included in final point estimates and confidence intervals.

16.32 Secondary Outcome Analyses (to be evaluated in each arm independently)

16.321 The overall response rate will be estimated by the number of patients who achieve an sCR, CR, VGPR or PR divided by the total number of evaluable patients. Exact binomial 95% confidence intervals for the true success proportions will be calculated.

16.322 The rate of  $\geq$  VGPR will be estimated by the number of patients with a VGPR, CR, or sCR divided by the total number of evaluable patients. Exact binomial 95% confidence intervals for the true success proportions will be calculated.

16.323 Overall survival is defined as the time from registration to death due to any cause. The distribution of overall survival will be estimated using the method of Kaplan-Meier.

16.324 Progression-free survival is defined as the time from registration to the earliest date of documentation of disease progression or death due to any cause. The distribution of progression-free survival will be estimated using the method of Kaplan-Meier

16.325 Adverse Events: All eligible patients that have initiated treatment will be considered evaluable for assessing adverse event rate(s). The maximum grade for each type of adverse event will be recorded for each patient, and frequency tables will be reviewed to determine patterns. Additionally, the relationship of the adverse event(s) to the study treatment will be taken into consideration

16.33 Correlative Analyses: Due to the small overall sample size, the results of these analyses will be considered exploratory and hypothesis-generating in nature.

- 16.331 Minimal residual disease will be assessed on bone marrow aspirate in all patients achieving CR. The proportion of patients who achieve MRD negative status will be estimated by the number of patients who are MRD negative divided by the total number of evaluable patients. Exact binomial 95% confidence intervals for the true MRD negative rate will be calculated.
- 16.332 The FACT/GOG neurotoxicity questionnaire will be completed by patients at baseline, after each cycle for the first 4 cycles, and then every three cycles. Patients will be evaluated by overall score for each questionnaire at each time point and changes over time will be calculated. These measures will be correlated with outcome using Fisher's exact test and Kaplan-Meier methods where appropriate.

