#### **1. Management of Safety Data**

This Study has been designated as an interventional study. As such, all adverse events for Janssen Medicinal Products regardless of causality and special situations excluding those from subjects not exposed to a Janssen Medicinal Product and product quality complaints with or without an adverse event as described in this Exhibit will be reported from the time a

subject has signed and dated an Informed Consent Form (ICF) until completion of the subject's last study-related procedure (which may include contact for follow-up safety). Serious adverse events will be reported for 30 days after the last dose of study drug.

For the purposes of this study, the Janssen medicinal product is: DARZALEX™ (daratumumab)

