#### **6. Procedures for Reporting Safety Data and Product Quality Complaints (POCs) for Janssen Medicinal Products to Janssen Scientific Affairs, LLC**

All adverse events and special situations, whether serious or non-serious, related or not related, following exposure to a Janssen medicinal product are to be documented by the investigator and recorded in the CRF and in the subject's source records. Investigators must record in the CRF their opinion concerning the relationship of the adverse event to a Janssen medicinal product.

All (serious and non-serious) adverse events reported for a Janssen medicinal product should be followed-up in accordance with clinical practice.

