#### 13.8 Ineligible

A patient is deemed *ineligible* after registration, it is determined that at the time of registration, the patient did not satisfy each and every eligibility criteria for study entry. The patient may continue treatment off-protocol at the discretion of the physician as long as there are no safety concerns, and the patient was properly registered. The patient will go directly to the event-monitoring phase of the study (or off study, if applicable).

- If the patient received treatment, all data up until the point of confirmation of ineligibility must be submitted. Event monitoring will be required per [Section 4.2](#) of the protocol.
- If the patient never received treatment, on-study material and the End of Active Treatment/Cancel Notification Form must be submitted. No further data submission is necessary.

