#### 13.9a Major violation

A patient is deemed a *major violation*, if protocol requirements regarding treatment in Cycle 1 of the initial therapy are severely violated that evaluability for primary end point is questionable. All data up until the point of confirmation of a major violation must be submitted. The patient will go directly to the event-monitoring phase of the study. The patient may continue treatment off-protocol at the discretion of the physician as long as there are no safety concerns, and the patient was properly registered. Event monitoring will be required per [Section 4.2](#) of the protocol.

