#### 16.4 Data & Safety Monitoring:

- 16.41 The principal investigator(s) and the study statistician will review the study at least twice a year to identify accrual, adverse event, and any endpoint problems that might be developing. The Mayo Clinic Cancer Center (MCCC) Data Safety Monitoring Board (DSMB) is responsible for reviewing accrual and safety data for this trial at least twice a year, based on reports provided by the MCCC Statistical Office.
- 16.42 Adverse Event Stopping Rules (to be evaluated in each arm independently): The stopping rules specified below are based on the knowledge available at study development. We note that the Adverse Event Stopping Rule may be adjusted in the event of either (1) the study re-opening to accrual or (2) at any time during the conduct of the trial and in consideration of newly acquired information regarding the adverse event profile of the treatment(s) under investigation. The study team may choose to suspend accrual because of unexpected adverse event profiles that have not crossed the specified rule below.

Accrual will be temporarily suspended to this study if at any time we observe events with an attribution of possibly, probably, or definitely related to study treatment that satisfy one of the following:

- if 5 or more patients in the first 13 treated patients experience a grade 4 or higher non-hematologic adverse event
- if after the first 13 patients have been treated, 40% of all patients experience a grade 4 or higher non-hematologic adverse event.

We note that we will review grade 4 and 5 adverse events deemed "unrelated" or "unlikely to be related", to verify their attribution and to monitor the emergence of a previously unrecognized treatment-related adverse event.

16.5 Results Reporting on ClinicalTrials.gov:

At study activation, this study will have been registered within the “ClinicalTrials.gov” website. The Primary and Secondary Endpoints along with other required information for this study will be reported on [REDACTED] For purposes of timing of the Results Reporting, the initial estimated completion date for the Primary Endpoint of this study is 5 years after the study opens to accrual. The definition of “Primary Endpoint Completion Date” (PECD) for this study is at the time all patients registered have achieved a confirmed complete response or have discontinued treatment without achieving a confirmed complete response.

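### Final adverse-event rates leave out patients who were dosed and later found ineligible

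*Combined protocol and SAP*

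**What the plan says.** Section 16.325 sets the denominator for adverse-event rates: "All eligible patients that have initiated treatment will be considered evaluable for assessing adverse event rate(s". It then tabulates the maximum grade of each type of event per patient. Toxicity is one of the secondary goals in section 2.2, so these rates are a planned result of the trial.

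Section 13.8 makes ineligibility a status that can be assigned after registration, when it emerges that a criterion was not met at entry. It allows for such a patient having been dosed: "If the patient received treatment, all data up until the point of confirmation of ineligibility must be submitted". The patient then moves to event monitoring.

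Section 10.62 has no eligibility limit. Under item 6, all adverse events "following exposure to a Janssen medicinal product are to be documented by the investigator and recorded in the CRF". Under item 1: "Serious adverse events will be reported for 30 days after the last dose of study drug".

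The stopping rule in 16.42 also has no eligibility limit. Its first part applies "if 5 or more patients in the first 13 treated patients experience a grade 4 or higher non-hematologic adverse event"; its second applies "if after the first 13 patients have been treated, 40% of all patients experience a grade 4 or higher non-hematologic adverse event".

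**The concern.** Exposure to the four drugs does not depend on whether every entry criterion was met. A safety table normally describes everyone who was exposed. Under 16.325 a dosed patient drops out of the rates once found ineligible, although the plan has gathered the data.

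Common toxicities would hardly be affected. What could be lost is a rare serious event that happens to fall in an ineligible patient: in an arm of at most 40, a single such event decides whether the table shows the event at all. Some entry criteria also concern safety, such as creatinine clearance, neutrophils, platelets and bilirubin in 3.12, neuropathy in 3.25 and cardiovascular disease in 3.28. A patient who missed one of these might carry more risk than average, but the documents contain no data on that, so no direction of bias can be claimed.

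**Working it through.** **1. Who is lost.** Setting the sections side by side:

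| Patient | Dosed? | In the 16.325 set? | Source |
|---|---|---|---|
| Eligible, treated | yes | yes | 16.325 |
| Major violation, eligible | yes | yes (16.325 does not exclude them) | 13.9a, 16.325 |
| Ineligible, treated | yes | **no** | 13.8, 16.325 |
| Cancelled | no | no, correctly | 13.9b |

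Nothing else in section 16 restores the third row. Section 16.313 brings only over-accrued patients into the final estimates, and it concerns the primary outcome.

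**2. How many.** Section 16.12 plans 36 evaluable patients and 4 spare places per arm: 36 + 4 = 40. The 4 cover ineligibility, cancellation, major violation and other reasons, and no split is given. If the plan is met, the treated-but-ineligible number *k* lies between 0 and 4 per arm. Cancelled patients were never dosed, and major violations stay in the adverse-event set unless they are also ineligible. A value of *k* below 4 is therefore likely, and 0 is possible.

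**3. A rare event.** Assume 40 treated and *k* = 2, so the 16.325 set is 40 − 2 = 38. Suppose one fatal event occurs, in an ineligible patient. Exact (Clopper-Pearson) 95% limits:
- As 16.325 would report it: 0/38 = 0%. Upper limit 1 − 0.025^(1/38) = 9.3%, so the interval is 0 to 9.3%.
- In all treated patients: 1/40 = 2.5%. Lower limit 1 − 0.975^(1/40) = 0.1%. The upper limit solves P(X ≤ 1 | 40, p) = 0.025, giving 13.2%.

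The intervals overlap heavily. The substantive difference is that the event is absent from one table and present in the other.

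**4. A common event.** Suppose 8 eligible patients have the event and 40 are treated. The reported rate is 8/(40 − *k*). The rate in all treated patients runs from 8/40, if no ineligible patient had it, to (8 + *k*)/40, if all did.

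| *k* (assumed) | Reported | All treated, range |
|---|---|---|
| 0 | 8/40 = 20.0% | 20.0% |
| 1 | 8/39 = 20.5% | 20.0% to 22.5% |
| 2 | 8/38 = 21.1% | 20.0% to 25.0% |
| 4 | 8/36 = 22.2% | 20.0% to 30.0% |

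At *k* = 2 the exact interval for 8/38 is 9.6 to 37.3%, about 28 percentage points wide. The largest possible shift is 25.0 − 21.1 = 3.9 points. The row *k* = 4 is the extreme in which every spare place went to a dosed, ineligible patient.

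**The case against.** The strongest reply is that little is at stake. Section 6.3 checks eligibility before registration is accepted, so there may be no treated-but-ineligible patient. No event goes unreported either: deaths within 30 days of the last dose are reported whatever their attribution (10.412, 10.523), all adverse events go to the daratumumab supplier (10.62), and the DSMB reviews safety at least twice a year (16.41). None of this is limited to eligible patients. What remains is a prespecified denominator in a descriptive table. All of that stands, and it is why the point is minor. It does not remove the point: prespecifying the set does not make the published rates cover everyone exposed.

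A second reply is that the remedy has a cost. Ineligible patients leave for event monitoring, so each would count fully in the denominator after shorter routine observation. That is correct and should be disclosed beside the rates.

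Two stronger readings are tempting, and the documents support neither.
- *A reader might infer that an arm could reach the 40% limit in 16.42 while its final table shows a rate below that limit.* The two sections measure different things. Section 16.42 counts patients with any grade 4 or higher non-hematologic event at least possibly related to treatment, as a trigger for suspending accrual. Section 16.325 tabulates maximum grade by event type, and no table of the 16.42 composite is planned. Once 40 patients have been treated, that arm has no accrual left to suspend. All that can be said is that the two sets are worded differently.
- *A reader might infer that excluding ineligible patients and major violations distorts the complete response result.* The evaluable set for response is stated in advance and is the same in 16.11 and 16.311. Under 13.9a a major violation concerns treatment in Cycle 1, and no passage ties exclusion to response. The lack of a sensitivity analysis there is not an error.

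**Conclusion.** The point holds as a minor one. Followed as written, 16.325 omits dosed patients later found ineligible from a stated secondary result, although their data are collected. The gap is confined to the final adverse-event tables; safety oversight during the trial is not impaired.

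The wording issue is certain. Its practical size is not: it depends on an unstated number of patients, from 0 to 4 per arm and probably below 4. The rare-event illustration (0/38 instead of 1/40) assumes both that 2 of 40 were ineligible and that the event fell in one of those two. For common events the change is small against the sampling error.

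**What to change.** Replace the first sentence of 16.325 with: *All patients who receive any dose of study treatment are included in adverse-event analyses, regardless of eligibility.* Add a footnote to the tables giving the number of ineligible patients included and stating that their routine data end when ineligibility is confirmed.

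The cost is one sentence and one footnote. No new data are needed: 13.8 already requires data up to confirmation, and 10.62 requires serious events for 30 days after the last dose. The set then also matches the treated-patient wording of 16.42. The drawback is the shorter routine observation of these patients, which can slightly lower cumulative rates; the footnote lets a reader judge this. The response analyses and the 13-of-36 decision rule are not touched.

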### 3.2 Exclusion Criteria

3.21 MGUS or smoldering myeloma.

3.22 Diagnosed or treated for another malignancy  $\leq$  2 years prior to registration or previously diagnosed with another malignancy and have any evidence of residual disease. **NOTE:** Patients with nonmelanoma skin cancer or carcinoma in situ of any type are not excluded if they have undergone complete resection.

3.23 Any of the following because this study involves an investigational agent whose genotoxic, mutagenic and teratogenic effects on the developing fetus and newborn are unknown:

- Pregnant women
- Nursing women
- Men or women of childbearing potential who are unwilling to employ adequate contraception

3.24 Other concurrent chemotherapy, or any ancillary therapy considered investigational. **NOTE:** Bisphosphonates are considered to be supportive care rather than therapy, and are thus allowed while on protocol treatment.

3.25 Peripheral neuropathy  $\geq$  Grade 2 on clinical examination or grade 1 with pain during the screening period.

3.26 Major surgery  $\leq$  14 days prior to registration.

3.27 Systemic treatment with strong CYP3A4 inducers (rifampin, rifapentine, rifabutin, carbamazepine, phenytoin, phenobarbital, St. John's wort)  $\leq$  14 days prior to registration.

3.28 Evidence of current uncontrolled cardiovascular conditions, including hypertension, cardiac arrhythmias, congestive heart failure, unstable angina, or myocardial infarction  $\leq$  6 months. Note: Prior to entry, any ECG abnormality at screening must be documented by the investigator as not medically relevant.

3.29a Radiotherapy  $\leq$  14 days prior to registration. **NOTE:** If the involved field is small, 7 days will be considered a sufficient interval between treatment and administration of the ixazomib

3.29b Known human immunodeficiency virus (HIV) positive.

- 3.29c Known hepatitis B surface antigen-positive status, or known or suspected active hepatitis C infection.
- 3.29d Any serious medical or psychiatric illness that could, in the investigator's opinion, potentially interfere with the completion of treatment according to this protocol.
- 3.29e Known allergies, hypersensitivity, or intolerance to corticosteroids, monoclonal antibodies or human proteins, or their excipients (refer to respective package inserts or Investigator's Brochure), or known sensitivity to mammalian-derived products.

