6.8 Baseline symptoms

All required baseline symptoms (see Section 10.5) must be documented and graded.

6.9a Study drug

Study drug is available on site.

6.9b Blood kits

Blood kit is available on site for this patient.

6.9c Patient questionnaire booklets

Patient questionnaire booklet is available on site; copies are not acceptable for this submission.

6.9d GCP

The clinical trial will be conducted in compliance with regulations (21 CFR 312, 50, and 56), guidelines for Good Clinical Practice (ICH Guidance E6), and in accordance with general ethical principles outlined in the Declaration of Helsinki; informed consent will be obtained from all participating patients; the protocol and any amendments will be subject to approval by the designated IRB prior to implementation, in accordance with 21 CFR 56.103(a); and subject records will be stored in a secure location and subject confidentiality will be maintained. The investigator will be thoroughly familiar with the appropriate use of the study drug as described in the protocol and Investigator's Brochure. Essential clinical documents will be maintained to demonstrate the validity of the study and the integrity of the data collected. Master files should be established at the beginning of the study, maintained for the duration of the study and retained according to the appropriate regulations.

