### 8.51 Daratumumab-Related Toxicity Management

Refer to Section 9.9i for details on management of infusion-related reactions.

ONLY if any of the following criteria are met and the event cannot be ascribed to the other drugs, the daratumumab infusion must be omitted to allow for recovery from toxicity. The criteria for a dose omit are:

- Grade 4 thrombocytopenia or Grade 3 thrombocytopenia with bleeding
- Grade 4 neutropenia, if this is the second occurrence despite growth factor support
- Febrile neutropenia of any grade
- Neutropenia with infection, of any grade
- Grade 3 or higher nonhematologic toxicities with the following exceptions:
  - Grade 3 nausea that responds to antiemetic treatment within 7 days
  - Grade 3 vomiting that responds to antiemetic treatment within 7 days
  - Grade 3 diarrhea that responds to antidiarrheal treatment within 7 days
  - Grade 3 fatigue that was present at baseline or that lasts for <7 days after the last administration of daratumumab
  - Grade 3 asthenia that was present at baseline or that lasts for <7 days after the last administration of daratumumab

If a daratumumab administration does not commence within the prespecified window (Table) of the scheduled administration date, then the dose will be considered a missed dose. Administration may resume at the next planned dosing date.

Table 8.6 Daratumumab-Related Toxicity Management

Cycles	Frequency	Dose Held	Dosing Re-start
1 and 2	Weekly (q1wk)	>3 days	next planned weekly dosing date
3 to 6	Biweekly (q2wks) 	>1 week	next planned biweekly dosing date
7+	Every 4 weeks (Q4W)	>2 weeks	next planned every 4 weeks dosing date

A missed dose will not be made up. Doses of daratumumab may be delayed up to 4 weeks. If a dose is delayed, then the dates of the subsequent doses must be adjusted. Any adverse event deemed to be related to daratumumab and unrelated to lenalidomide, ixazomib or dexamethasone that requires a dose hold of more than 4 weeks will result in permanent discontinuation of daratumumab.

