10.5 Required routine reporting

10.51 Adverse events to be graded at each evaluation and pretreatment symptoms/conditions to be evaluated at baseline per the CTCAE v4.0 grading unless otherwise stated in the table below:

CTCAE SYSTEM/ORGAN/CLASS	Adverse event/Symptoms	Baseline	Each evaluation
Investigations	Creatinine increased	X	X
	Neutrophil count decreased	X	X
	Platelet count decreased	X	X
General disorders and administration site conditions	Fatigue	X	X
	Infusion related reaction		X
Gastrointestinal Disorders	Nausea	X	X
	Vomiting	X	X
	# of Stools	X	
	Diarrhea		X
Infections and infestations	Sepsis	X	X
Blood and lymphatic system disorders	Febrile neutropenia	X	X
Skin and subcutaneous tissue disorders	Rash- maculopapular	X	X
Nervous system disorders	Peripheral sensory neuropathy	X	X
	Peripheral motor neuropathy	X	X

10.52 Submit via appropriate MCCC Case Report Forms (i.e., paper or electronic, as applicable) the following AEs experienced by a patient and not specified in Section 10.6:

10.521 Grade 2 AEs deemed *possibly, probably, or definitely* related to the study treatment or procedure.

10.522 Grade 3 and 4 AEs regardless of attribution to the study treatment or procedure.

10.523 Grade 5 AEs (Deaths)

- Any death within 30 days of the patient's last study treatment or procedure regardless of attribution to the study treatment or procedure.
- Any death more than 30 days after the patient's last study treatment or procedure that is felt to be at least possibly treatment related must also be submitted as a Grade 5 AE, with a CTCAE type and attribution assigned.

10.53 Refer to the instructions in the Forms Packet (or electronic data entry screens, as applicable) regarding the submission of late occurring AEs following completion of the Active Monitoring Phase (i.e., compliance with Test Schedule in Section 4.0).

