## **2. Definitions**

### **2.1. Adverse Event (AE)**

An adverse event is any untoward medical occurrence in a clinical study subject administered a medicinal (investigational or non-investigational) product. An adverse event does not necessarily have a causal relationship with the treatment. An adverse event can therefore be any unfavorable and unintended sign (including an abnormal finding), symptom, or disease temporally associated with the use of a medicinal (investigational or non- investigational) product, whether or not related to that medicinal (investigational or non-investigational) product. (Definition per International Conference on Harmonisation [ICH])

This includes any occurrence that is new in onset or aggravated in severity or frequency from the baseline condition, or abnormal results of diagnostic procedures, including laboratory test abnormalities.

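### Section 16.325 tabulates maximum adverse event grades without using the baseline grades the protocol collects, so a literal table overstates mainly the low-grade rates of the solicited terms

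*Combined protocol and SAP*

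**What the plan says.** Section 16.325 gives the whole adverse event analysis. The population is eligible patients who started treatment. The summary is: "The maximum grade for each type of adverse event will be recorded for each patient, and frequency tables will be reviewed to determine patterns". It closes: "Additionally, the relationship of the adverse event(s) to the study treatment will be taken into consideration". Neither this section nor the rest of Section 16 mentions baseline grade, change from baseline or treatment-emergent events in connection with adverse events.

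The baseline data exist. Section 6.8 states: "All required baseline symptoms (see Section 10.5) must be documented and graded". Section 10.51 covers "Adverse events to be graded at each evaluation and pretreatment symptoms/conditions to be evaluated at baseline", using CTCAE version 4.0. Its table marks creatinine, neutrophils, platelets, fatigue, nausea, vomiting, sepsis, febrile neutropenia, maculopapular rash, and sensory and motor neuropathy for both baseline and each evaluation. Diarrhea has a stool count at baseline and a grade afterwards. Infusion reaction has no baseline entry.

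Events outside that list are handled differently. Under Section 10.52, Grade 2 events are submitted only if at least possibly related, and Grade 3 and 4 events regardless of attribution.

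One definition refers to baseline. Section 10.62, item 2.1, after defining an adverse event broadly, adds: "This includes any occurrence that is new in onset or aggravated in severity or frequency from the baseline condition".

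**The concern.** Because the 10.51 terms are graded at each evaluation whether or not they have changed, a stable pretreatment symptom acquires an on-study grade, and the maximum picks it up. Footnote 11 to the Section 4.1 schedule, attached to the induction column, also lets baseline values stand in for Cycle 1.

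Some baseline findings are to be expected in this population. Entry allows creatinine clearance down to 30 mL/min and platelets down to 75,000/mm³ (3.12), and one prior cycle of any regimen (3.15). Neuropathy is excluded only at or above "Grade 2 on clinical examination or grade 1 with pain during the screening period" (3.25), so painless Grade 1 neuropathy may enter. No criterion limits baseline fatigue. Appendix I makes renal insufficiency a myeloma-defining event.

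Toxicity is a stated secondary goal (Section 2.2), and there is no untreated comparator to show how much of an any-grade rate is the disease rather than the drugs. A reader of the final table could take persisting myeloma symptoms for regimen toxicity.

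**Working it through.** **The plan's own figures.** The plan states no figure for the adverse event table. Its stated design figures concern the response rule of at least 13 successes in 36. Exact binomial tails at true rates of 0.25, 0.30, 0.35, 0.40 and 0.45 are 0.0922, 0.2635, 0.5068, 0.7385 and 0.8933. These match the 0.09, 0.26, 0.51, 0.74 and 0.89 in Section 16.22. None of them uses adverse event grades, so nothing below alters them.

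**The rule applied to example patients.**

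- Painless Grade 1 sensory neuropathy at baseline and Grade 1 at every evaluation: the raw table counts Grade 1, although nothing is new or worse.
- Grade 3 fatigue at baseline, improving to Grade 2 at the first evaluation and never higher again: the raw table counts Grade 2, although the patient improved.
- No neuropathy at baseline, Grade 1 in a later cycle: the raw table counts Grade 1, and this is a new event.

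The raw table cannot tell the first patient from the third.

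**Illustrative size.** The documents give no baseline prevalence, so both inputs are assumptions:

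- b = fraction of patients with the symptom at baseline and still present at a post-baseline evaluation;
- t = fraction with a new or worsened event, independent of b.

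Raw any-grade rate = 1 − (1 − b)(1 − t) = b + (1 − b)t. Baseline-adjusted rate = t. Excess = b(1 − t).

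With t = 20%, counts are shown for 36 patients. The adverse event denominator may differ slightly from 36, but the percentages do not depend on it.

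| b | Raw rate | Excess (points) | Raw count of 36 | New or worsened, of 36 |
|---|---|---|---|---|
| 10% | 0.10 + 0.90 × 0.20 = 28% | 8 | 10.1 | 7.2 |
| 20% | 0.20 + 0.80 × 0.20 = 36% | 16 | 13.0 | 7.2 |
| 30% | 0.30 + 0.70 × 0.20 = 44% | 24 | 15.8 | 7.2 |

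The excess is about 3, 6 and 9 patients. For the same b values, t = 10% gives raw rates of 19%, 28% and 37%, and t = 40% gives 46%, 52% and 58%. Taking b up to 50% and t from 10% to 40%, the excess runs from 6 points (b = 10%, t = 40%) to 45 points (b = 50%, t = 10%).

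**Where the effect falls.** It is confined mainly to the 10.51 terms, because Section 10.52 does not collect Grade 1 events outside the list and filters Grade 2 events by attribution. It is mainly low-grade, because eligibility limits baseline neuropathy, neutrophils and platelets. The stopping rule in Section 16.42 counts only non-hematologic events of Grade 4 or higher that are at least possibly related, so persisting low-grade symptoms do not reach it.

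**The case against.** The strongest reply is that Section 16.325 is silent and does not instruct anyone to count baseline symptoms. That is correct. Section 10.51 also words adverse events at each evaluation separately from pretreatment conditions, so there is no textual basis for putting the baseline record itself into the maximum. What remains is that an unchanged symptom is still graded after baseline, and the stated maximum-grade rule has no step to remove it.

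A second reply is that attribution handles it, since a stable symptom could be classed as unlikely or unrelated and set aside. It might be, but 16.325 gives no rule for using attribution, whereas 16.42 shows the plan writing an explicit filter when it wants one. Attribution is also a judgment of cause, not a comparison with baseline.

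A reader might infer that 16.325 contradicts the protocol's definition of an adverse event. The documents do not support that. The wording in 10.62 is inclusive rather than exclusive, belongs to one industry partner's reporting section and is not cited in Section 16. For the same reasons it does not supply the missing comparison.

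Some tempting examples are weak. Diarrhea already has a baseline stool count, and ECOG status is not a 10.51 term. The exception in 8.51 for "Grade 3 fatigue that was present at baseline" belongs to a daratumumab omission rule and says nothing about how often this occurs. It does show, as do the references to baseline severity in 8.11 and newly developed neuropathy in 8.2, that the protocol uses baseline where it thinks of it.

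Two further points stand. A raw maximum-grade table is a legitimate all-cause summary that helps comparison with historical series. And a filter that only asked whether the grade exceeds baseline would drop a symptom that resolved and then returned on treatment at its baseline grade, which could be real toxicity.

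**Conclusion.** The point holds as a weakness in a descriptive secondary analysis. Followed literally, the stated rule gives an overstated any-grade rate for the solicited terms, and the data needed for a better one are already collected. The overstatement is 8 to 24 percentage points if 20% of patients have a new or worsened event and 10% to 30% carry a persisting baseline symptom. These fractions, their independence and the persistence of the symptom are assumptions; the true size cannot be derived from the documents. No Grade 3 or higher inflation has been quantified.

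A reader might go further and infer that the trial's safety decisions or its conclusion on activity are compromised. They are not: the primary endpoint, sample size and power do not use adverse event grades, and the stopping rule is essentially unaffected. A reader might also infer a biased toxicity comparison between Arms A and B. Section 16.32 evaluates each arm independently and plans no such test. An imbalance in baseline symptoms between the sequentially accrued arms could mislead an informal side-by-side reading, but nothing in the documents shows that one exists.

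**What to change.** Keep the raw maximum-grade table and add to Section 16.325:

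> For the terms graded at baseline under 10.51, the maximum post-baseline grade will also be tabulated for patients whose post-baseline grade exceeds their baseline grade, or whose baseline event resolved and then recurred on treatment; the baseline grade distribution will be shown alongside.

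The recurrence clause keeps events that a simple above-baseline filter would lose. Diarrhea and infusion reaction, which have no baseline grade, stay in the raw table.

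The cost is one sentence, one extra table and a merge with baseline grades already required; no new data are collected. The baseline-adjusted rates will be less comparable with historical raw maximum-grade tables, which the retained raw table covers.
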